Primary objective	To determine treatment effect on caregiver burden measured as Resource Utilization Dementia (RUD), and the Relative Stress Scale (RSS). Based on the correlation coefficient, we will use all three subcategories of RUD separately. Total score will be used when assessing RSS. Further, we will evaluate the economic consequences of the treatment by calculating Incremental Cost-Effectiveness Ratio (ICER) and quality adjusted life years (QALY).
Secondary objectives	To determine treatment effect on quality of life (QoL) using the European Quality of Life – 5 dimension – 5 levels (EQ-5D-5L), EQ-5D-VAS scale, Quality of Life in Alzheimer's disease scale (QoL-AD); neuropsychiatric symptoms in dementia using the Neuropsychiatric Inventory 12 item (NPI-12), agitation in dementia using Cohen-Mansfield Agitation Inventory (CMAI), depression in old age (Geriatric Depression Scale - GDS), functional level for instrumental and personal activities (ADL and IADL), and the caregiver rating of clinical meaningful change using Clinical Global Impression of Change (CGIC).
Exploratory objectives	
In line with total score of RSS, we will also explore the treatment effect on both single and clustered items.
 
In line with total score of QoL based instruments (EQ-5D-5L, QoL-AD, QoL – CG, GDS), we will also explore the treatment effect on both single and clustered items
 
To assess the effect on pain in dementia using the Mobilization – Observation – Behavior – Intensity Dementia Pain Scale (MOBID-2)
 
To determine the characteristics of the dyads who had the highest improvement in RUD and RSS, i.e., those who benefitted the most from the intervention.

Endpoints	
Primary endpoint: Change in caregiver burden and informal care time among the caregivers in the intervention group during active intervention period, and the follow-up. Change in Cost-efficiency of treatment.
 
Secondary endpoint: Improvement in QoL for both PwD and caregivers. Reduction in neuropsychiatric symptoms in dementia and functional level during active intervention period and follow-up.
 
Exploratory endpoint: Reduction in pain during active intervention period.

Treatments	Allocation to municipal coordinator delivering the multicomponent LIVE intervention (L:learning, I: innovation, V: volunteering and E:empowerment) or care as usual.
Number of patients	315 dyads will be screened to achieve at least 105 dyads per municipality.

Safety analysis	Not applicable

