Efficacy: primary	x		
Efficacy: secondary	x		x
Efficacy: other	x	x	x

General Statistical Methods and Definitions

General statistical methods

The statistical analysis will be presented by treatment group for the different analysis sets as outlined in section 4.

Stepped wedge design (SWD) do not strictly feature a treatment and control group, and thus, the summary statistics will include all participants at baseline, and the characteristics according to intervention sequences.

Continuous variables will be summarized using descriptive statistics (means and interquartile ranges), and categorical variables will be presented by frequencies and percentages. A table will present the number of caregivers and PwD with the following data: missing values, mean, median, standard deviation and confidence intervals.

Means and median as well as percentages will be presented with 1 additional decimal place and standard deviation by 2 additional decimals.

If the number of PwD or caregivers in a category is 0, then percentage will not be displayed.

P-values will be reported to 3 decimal places.

Unless otherwise specified, all statistical tests will be two-sided.

Causal model

Due to the longitudinal structure of the collected trial data, we considered the following linear mixed model to estimate and identify the treatment effect due to the intervention. Our SWD, consisting of $j = 3$ municipalities and 3 steps, is a closed cohort design, and thus, time related confounders are important to adjust for [5] when assessing treatment effect.

Mixed-effects regression is one of the most common approaches when estimating the intervention effect in SWD [6, 7]. In our design, we will consider the following model as our primary analysis model, assuming a constant treatment effect.

$$(1) Y_{ijt} = \beta_0 + O_{ijt}\beta_1 + X_{ijt}\beta_2 + b_i + \epsilon_{ijt}$$

where notation Y_{ijt} refers to the primary outcome caregiver burden (RUD and RSS), elaborated in section 3 Study Design, for individual i nested in municipality j at time point t . O_{ijt} is the treatment indicator (effect of receiving assistance from a municipality coordinator) and β_1 is the average treatment effect parameter of interest. Since the study collects repeated observations from the same participants, we consider a longitudinal regression model that adjusts for participant-level random effect, $b_i \sim N(0, \sigma_b^2)$, which corresponds to a compound symmetric correlation structure.

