The definition of treatment assignment as specified in section “Analysis sets” will be used in this section, too.

Deviations from the randomized treatment sequence occurred under the first Covid-19 lockdown, see section Modification History, Changes to the study protocol

Treatment duration

Each municipal coordinators are writing logs, and we will collect the data and calculate total hours of care by the coordinator, divided into different categories.

Descriptive statistics for the total hours of care by the coordinators will be presented.

Delivery of the intervention

One coordinator from the municipal per dyad

Efficacy

Primary efficacy analysis

The primary efficacy analysis variable caregiver burden is based on two variables. The first is RUD, divided in three categories: number of hours the last 30 days invested in personal, instrumental and supervisory care. The second is RSS measured as total score but also

specific and clustered items. Lower hours of informal care as well as lower score of RSS, indicates reduction in caregiver burden.

The null hypothesis states that there are no differences in burden and resource utilization between the LIVE intervention and usual care. The primary alternative hypothesis (H1) states that the LIVE intervention will improve caregiver burden and resource utilization compared with usual care. The secondary alternative hypothesis (H2) is that the LIVE intervention will provide more cost-efficient services than usual care.

H0: LIVE treatment = control

H1: LIVE treatment > control

H2: cost efficiency > control

where LIVE treatment denotes the proportion of caregivers experiencing improvement in care burden. The primary hypothesis will be statistically assessed by means of a χ^2 test on the one-sided significance level of 2.5% (corresponding to 5% two-sided).

We will plot the regression line to visualize the parallel effect for both treatment group and control group.

The significance level will be set to 2.5% (one-sided, corresponding to 5% two-sided), the corresponding level of one-sided CI is 97.5% (corresponding to 95% two-sided).

Missing data

We will pre-specify a list of baseline covariates that are likely associated with the missingness and the outcome, and adjust for these covariates in our primary analyses. This covariate-adjusted analysis will be valid under the missing at random (MAR) mechanism.

Sensitivity and robustness tests of regression analyses and economic evaluation

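### The SAP states the primary endpoint in three incompatible forms, and equation (1), which should settle the matter, shows no calendar-period effects

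*SAP*

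**What the plan says.** Three places in the SAP define what the primary analysis is about.

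- **Study Design, Endpoints row.** The primary endpoint is "Change in caregiver burden and informal care time among the caregivers in the intervention group during active intervention period, and the follow-up". No usual-care comparison is named. The Primary objective row of the same table does ask for a treatment effect on RUD and RSS.
- **Causal model.** The outcome symbol in equation (1) is explained with the words "refers to the primary outcome caregiver burden (RUD and RSS), elaborated in section 3 Study Design, for individual i nested in municipality j at time", so it stands for a repeated level, and the reader is sent back to Study Design for its definition. The coefficient β1 of the treatment indicator "is the average treatment effect parameter of interest". The section says that time-related confounders matter in a closed-cohort stepped wedge. Equation (1) nevertheless contains only an intercept, the treatment indicator, covariates, a participant random effect and error. The covariates listed for it are demographic, socio-economic and clinical variables and the stratification variables.
- **Primary efficacy analysis.** RUD is the "number of hours the last 30 days invested in personal, instrumental and supervisory care", and RSS is a total score. The null hypothesis is that "there are no differences in burden and resource utilization between the LIVE intervention and usual care". Below H0 and H1, however, the compared quantity becomes the share of caregivers whose burden improves, tested by chi-square at one-sided 2.5%.

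**The concern.** A within-group change, a treated-versus-untreated difference in level, and a difference in proportion improved can give different answers from the same data. The SAP does not say which one is primary. The model's reference back to Study Design does not help, because an analyst who follows it arrives at the within-group wording.

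Taken literally, the Endpoints row cannot test the stated null hypothesis. Every sequence receives the intervention, so a change among treated caregivers has no comparator and includes whatever dementia and caregiving would have done anyway. The proportion improved has its own gap: the SAP gives neither a threshold for improvement nor the visit from which it is measured.

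The comparative model is the natural way out, but as written it does not fully separate treatment from time. In a stepped wedge, treated visits fall later than untreated ones. Without period terms, β1 absorbs part of any drift.

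**Working it through.** **The three forms side by side**

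| Place | Quantity | Comparator | Analysis named |
|---|---|---|---|
| Study Design, Endpoints | Change over intervention and follow-up | None | None |
| Causal model | RUD and RSS level at each visit | Untreated observations | Mixed model, β1 |
| Primary efficacy analysis | Hours and RSS score, then proportion improved | Usual care | Chi-square test |

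**Which form the sample size supports.** The inputs in Sample size estimation are a difference of 7 h/week, SD 20, 80% power and 5% significance. For two means, n per group = 2 × (1.960 + 0.842)² × 20² / 7² = 2 × 7.85 × 400 / 49 ≈ 128.2, so 129 per group and 258 in total. The SAP states 260, which matches. That number therefore rests on a between-condition difference in level. It was not derived for a within-group change or for a proportion improved.

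**What equation (1) does with a time trend.** Inputs:

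- From the SAP: 3 sequences, 5 periods, and within-individual correlation ρ = 0.1075, which is given for the post-hoc calculation on PADL.
- Assumed: equal sequences, the planned schedule, a treatment indicator that stays on during follow-up (consistent with the table under Intervention effect), no true effect, and a linear drift of s h/week per 6-month phase. The SAP gives no natural trend.

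Number the visits 0 to 4. The sequences are treated at 4, 3 and 2 visits, which is 9 of 15 cells. The visit numbers in treated cells sum to 10 + 9 + 7 = 26. Over all cells they sum to 3 × 10 = 30.

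Under compound symmetry the inverse covariance is proportional to I − cJ, where J is the all-ones matrix and c = ρ/(1 + 4ρ) = 0.1075/1.43 = 0.0752. With an intercept and the treatment indicator only, generalised least squares gives:

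- numerator: (26 − 90c) − (9/15) × 30 × (1 − 5c) = 8, because the terms in c cancel;
- denominator: (9 − 29c) − (81/15) × (1 − 5c) = 3.6 − 2c = 3.450.

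The bias in β1 is s × 8/3.450 = 2.32s:

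| Assumed drift per phase (h/week) | Bias in β1 (h/week) | Design difference (h/week) |
|---|---|---|
| 1 | 2.3 | 7 |
| 2 | 4.6 | 7 |
| 3 | 7.0 | 7 |

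The multiplier hardly depends on ρ: it is 2.22 at ρ = 0 and 8/3.267 = 2.45 at ρ = 0.5. Rising hours would hide a benefit, and falling hours would mimic one.

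**What period effects cost.** With period effects fitted, the 3.6 in the denominator becomes 4/3, because only the two visits at which the sequences differ contribute within-period information. Take 80 dyads per sequence (240 in total) and variance 400, so that 400 × (1 − ρ) = 357:

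- without period effects: SE = √(357 / (80 × 3.450)) = 1.14 h/week;
- with period effects: SE = √(357 / (80 × 1.183)) = 1.94 h/week.

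At an SE of 1.94, a difference of 7 lies 7/1.94 = 3.6 standard errors from zero. Under these inputs the model with period effects needs about 145 dyads for 80% power. That does not reproduce the SAP's post-hoc 240, so these SEs are illustrative and do not check that figure.

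**The case against.** An Endpoints row is a short label, and trialists often write change when they mean a treatment effect on repeated measures. The substance is fixed elsewhere: the objective asks for a treatment effect, the Treatments row names care as usual, β1 is the stated parameter of interest, and the null compares LIVE with usual care. This largely stands, and it limits the consequence.

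Two stronger readings are tempting, and the SAP does not support either.

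- **A reader might infer that the reported primary result would simply be the natural course of dementia.** No section plans a within-group test, so the Endpoints row alone would not produce that result.
- **A reader might infer a loss of precision from analysing change from month 0.** No change-score model is planned. If one were used in the five-visit design with period effects, its SE at 240 dyads would be 2.19 against 1.94 h/week for levels, and power for 7 h/week would still be about 89%. This is not a reason to act.

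It can also be said that period effects are implied, since the SAP names time-related confounding and cites stepped-wedge methods. That may be the intention, but neither the equation nor the covariate lists contain them. The secondary analysis by lockdown period lets the treatment effect vary; as described, it does not supply a common period effect.

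The objection does not remove the chi-square test on proportion improved, which stands as the formal test of the primary hypothesis beside a mixed model that is called primary.

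**Conclusion.** The concern holds as an inconsistency in the definition of the primary endpoint. The three forms are incompatible, one has no comparator, and the sample size matches only a comparison of levels. The consequence is ambiguity that leaves room to choose among results, which is worth correcting in a final SAP.

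The missing period term is the concrete route by which time could enter the treatment estimate. Its size is about 2.3 h/week of bias per 1 h/week of drift per phase, so a drift of 3 would equal the whole design difference. The drift is assumed. The figure also rests on the planned schedule, which the pandemic disrupted, and on covariates that absorb none of the trend; ADL function updated at each visit could absorb some. If the analysts fit period effects anyway, this bias does not arise, and the fault lies only in the written model.

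**What to change.** State one primary endpoint in the same words in the Endpoints row, the Causal model section and the Primary efficacy analysis section: the difference between LIVE and usual care in the level of RUD hours (for each of the three categories the SAP analyses separately) and of RSS total score, estimated by β1. Say that month 0 is kept as a repeated outcome record and is not subtracted.

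Amend equation (1) openly to include calendar-period fixed effects, and base the test of the primary hypothesis on β1 in place of the chi-square test. Label within-group change and proportion improved as descriptive or secondary. If proportion improved is kept, define the threshold and the reference visit.

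The cost is a small amendment to the written model and text, with no new data. Standard errors become wider, 1.94 against 1.14 h/week in the illustration above, but the smaller value belongs to an estimate that is unbiased only if there is no time trend.

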Planned enrolment	3 municipalities and 9 municipality districts

Sample size estimation

The required sample size calculated before recruitment of participants aimed to detect a difference of 7 h/week for the primary outcome RUD. Based on the literature[4], we assumed that the number of hours of informal care is 46 h/week with a standard deviation (SD) of 20 h/week. With 80% power and a significance level of 5%, the required sample size was estimated to be 260 dyads. To allow for 20% loss to follow-up, a total of 315 dyads, equaling 105 per municipality, must be included.

The post-hoc sample size calculations based on the outcome PADL showed that by treating the study as an individually randomized stepped wedge design[3], with 3 intervention sequences, 5 periods, effect size of 7h/week, outcome variance of 400, significance level of 5% and within-individual correlation of 0.1075 over the 24 month trial would require a total of 240 dyads to be included. To allow for 20% loss to follow-up, the sample size must reach 288 dyads.

Randomization, blinding and unblinding procedures

Block randomization was performed using a computerized random number generator to allocate individual dyads to the three intervention sequences. We will apply stratification to secure that about one third of the dyads in each treatment sequence will be recruited from each municipality. Research assistants, researchers conducting the analyses and other study personal conducting data collection will be blinded to the randomization order, the dyads will be blinded to group allocation until contacted by their coordinator at start of the intervention period. Given the practice change of the intervention, the municipality home care services and coordinators will be informed about allocation sequence when their clusters entered the intervention period.

Analysis Sets

Full Analysis Set (FAS)

The intention-to-treat population includes all randomized dyads who were assigned a coordinator by the municipality. The dyads will be analyzed separately (i.e., PwD and caregiver), dependent on outcome of interest.

This will be the primary analysis set for baseline summary statistics of demographics, primary, secondary and exploratory efficacy analysis as elaborated in section 10.

Municipal coordinator set (MCS)

All coordinators in all municipality districts

Usage overview of analysis sets table

Analyses	FAS	MCS	
Disposition			
Demographics and background	x		
Medical history			

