- Formal caregiver (whether dyads are receiving care by home nursing)
- Categories of caregiver burden intensity
- Categories of dementia diagnoses

Results from subgroups will be presented for the primary analyses.

Observation and analysis times

Study periods

Timeline															
Groups/participants	Inclusion period	Control group			Kristiansand 3, N=35			Bærum 3, N=35			Bergen 3, N=35				
					Kristiansand 2, N=35										
					Bærum 2, N=35										
					Bergen 2, N=35										
		Kristiansand 1, N=35						Follow up							
Number of months		0	1 2	3 4	5 6	7 8	9 10	11 12	13 14	15 16	17 18	19 20	21 22	23 24	
Date		01.09 2019		01.03 2020		01.09 2020		01.03 2021							

		STUDY PERIOD							
		Enrollment		Allocation	Post-allocation				Close-out
TIMEPOINT	-t	0		t1	t2	t3	t4	t5	
ENROLLMENT:									
Eligibilityscreen	x								
Informed consent	x								
Allocation		x							
INTERVENTIONS:									
1st group			x	x					
2nd group				x	x				
3rd group					x	x			
ASSESSMENTS:									
Baseline variables			x						
Outcome variables				x	x	x	x	x	

The stepped wedge randomized control design. A) The randomization in time takes place at month 0. First group (red) is in the intervention period from month 1 to 6, second group (yellow) from month 7 to 12, third group (green) from month 13 to 18. Implementation seminars will be held at month 0, 6 and 12, midway evaluation at month 3, 9 and 15. Data will be collected at baseline (month 0), after first intervention period (month 6-7), after second intervention period (month 12-13), after third intervention period (month 18-19) and at end of study at 24 months. B) Schedule of enrollment, interventions and assessments over the study period.

Demographics and Background Characteristics

Demographics and baseline characteristics

The following demographic characteristics will be presented descriptively and listed for both PwD and caregiver:

- Sex (male, female)
- Age in years
- Marital status (spouse, child)
- Work status (employed, unemployed, retired)
- Number of co-caregivers
- MMSE total score
- RUD (number of care hours the last 30 days)
- RSS total score
- NPI total score
- QoL total score

Date of informed consent and protocol version will be listed

Medical history

We will provide information on the number of years since formal diagnosis of dementia together with descriptive statistics.

Exposure and Compliance

Treatment groups

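### The totals of 315 and 288 dyads cover 17.5% and 16.7% loss, not the stated 20%, and the post-hoc figure of 240 is given without a power

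*SAP*

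**What the plan says.** The SAP's section on sample size estimation contains two calculations.

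- **Before recruitment.** The target is a difference of 7 h/week in RUD with an SD of 20 h/week. "With 80% power and a significance level of 5%, the required sample size was estimated to be 260 dyads". The enrolment target follows: "To allow for 20% loss to follow-up, a total of 315 dyads, equaling 105 per municipality, must be included".
- **Post hoc, on PADL.** The study is treated as an individually randomized stepped wedge with 3 sequences and 5 periods. The remaining inputs are "effect size of 7h/week, outcome variance of 400, significance level of 5% and within-individual correlation of 0.1075", and the result is that the trial "would require a total of 240 dyads to be included". Then: "To allow for 20% loss to follow-up, the sample size must reach 288 dyads". The list of inputs contains no power.

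Two other places bear on the figure of 315. The row on number of patients in the Study Design table reads "315 dyads will be screened to achieve at least 105 dyads per municipality". The timeline under Study periods shows cells of 35 dyads by municipality and sequence group, for example "Kristiansand 1, N=35".

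**The concern.** An allowance for 20% loss means that the required number remains once 20% of those enrolled have gone, so the required number is divided by 0.8. Both printed totals are lower than that division gives. The plan therefore claims protection against more attrition than its own numbers provide.

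The second issue is one of reporting. The figure of 240 comes directly after a calculation at 80% power, so a reader will tend to carry the 80% over and compare 240 with 260 as if both had the same power. The text does not say so, and the listed inputs do not by themselves lead to 240 at 80%.

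Sample-size statements are usually carried into the results paper, so both points are worth settling in the SAP.

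**Working it through.** **1. Reproducing 260.** Inputs: difference 7, SD 20, power 80%, significance level 5%. Two-sided testing is taken from the SAP's general statistical methods; a 1:1 two-group comparison is assumed.

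n per group = 2 × 20² × (1.960 + 0.842)² / 7² = 128.1, rounded up to 129, or 258 in total. The t-test version needs 129.1 per group, rounded up to 130, or 260 in total. The printed 260 is reproduced.

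**2. The loss allowance.** This needs only the printed numbers.

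| | First calculation | Post hoc |
|---|---|---|
| Required, N | 260 | 240 |
| Printed total, T | 315 | 288 |
| Left after 20% loss, T × 0.8 | 252 | 230.4 |
| Loss actually covered, 1 − N/T | 17.5% | 16.7% |
| Total for 20% loss, N / 0.8 | 325 | 300 |
| Shortfall | 10 | 12 |
| N × 1.2 | 312 | 288 |

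The figure of 288 is exactly 240 × 1.2, which points to multiplying by 1.2 where division by 0.8 was needed. The figure of 315 would fit 260 × 1.2 = 312 rounded up to nine cells of 35 (9 × 35 = 315), but that is an inference.

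**3. What the shortfall costs in the first calculation.** Two-group t-test power with the same inputs is 80.3% at 260 and 79.0% at 252.

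**4. What power could lie behind 240.** Take the listed inputs (variance 400, correlation 0.1075, difference 7, two-sided 5%) and sequences 01111, 00111 and 00011 in equal numbers. Fit by generalized least squares with a normal approximation: N = v × (1.960 + z_power)² / 7², where v is the variance of the effect estimate times the number of dyads. With period effects, a constant effect and compound symmetry, v = 905.3.

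- 80% power: 905.3 × (1.960 + 0.842)² / 49 = 145 dyads
- 90% power: 194 dyads
- 95% power: 240 dyads

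The constant effect and compound symmetry are what the SAP states under Causal model. Period effects are read in from its remark there on time-related confounding; equation (1) prints none. Other readings give other answers:

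| Model | Dyads at 80% power |
|---|---|
| No period term, as equation (1) is printed | 50 (82 at 95%) |
| Period effects, compound symmetry, separate active and follow-up effects | 149 (active), 251 (follow-up) |
| Period effects, correlation decaying to 0.1075 over 24 months, separate effects | 98 (active), 242 (follow-up) |

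So 240 matches 95% power under one model and is close to 80% for the follow-up effect under another. The text does not settle which was used.

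**5. Loss in the post-hoc calculation, under the constant-effect model with period effects.** Power is 95.0% at 240 and 94.2% at 230. The 230 is a worst case in which a lost dyad contributes no data. If 20% drop out evenly over the four later visits (assumed: 5% at each) and earlier visits are kept, 288 dyads give 96.7%.

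**The case against.** The case for leaving the text alone is that nothing of substance turns on it.

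- The totals fit a reading in which 20% is simply added, and the plan does not spell out its rule. That explains where 288 came from, but the allowance is stated as loss to follow-up, which is a share of those enrolled. On that meaning the figures are wrong.
- The first shortfall shrinks if one starts from the unrounded normal-approximation requirement of 256.3, since 256.3 / 0.8 = 320, about 5 more than 315. That is true, but the plan prints 260 as the requirement, and 320 is still above 315. It does nothing for 288.
- The planned mixed model keeps the earlier visits of dyads who drop out, and 315 exceeds the 300 needed against the plan's own stepped-wedge figure. Both points stand. They limit the consequence without making the printed allowance correct.
- The 95% reading of 240 depends on a chosen model. The primary endpoint covers both the active period and follow-up, and the correlation is given over the 24-month trial. That lends some support to the reading with separate effects and decaying correlation, where 240 is near 80%. This objection stands in full: 240 is not shown to be an error. What remains is that power and model are unreported.
- The difference between screened and included dyads is one of wording, not arithmetic. That is so, but it decides whether even 17.5% is available. If 315 is the number screened, any screen failure lowers the allowance further.

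**Conclusion.** The stated 20% allowance is wrong as written for both totals. They cover 17.5% and 16.7% loss, and are 10 and 12 dyads short of the 20% figures. This rests only on the printed numbers and on taking loss as a share of enrolled dyads; the 17.5% also assumes that all 315 are included and not merely screened. The point is minor: about one percentage point of power in the first calculation, with no doubt cast on the adequacy of the trial.

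The absent power for 240 is a gap in reporting, not a demonstrated miscalculation. Under the SAP's constant-effect, compound-symmetry model with period effects added, 240 corresponds to 95% power and should not be read as an 80% figure. Under other defensible models it may be close to 80%, so the authors have to say which model they used.

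**What to change.** In the section on sample size estimation:

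- Either state that 315 and 288 dyads allow for about 17.5% and 16.7% loss, or give 325 and 300 as the totals that 20% loss would require.
- Say whether 315 counts dyads screened or dyads included, and bring the Study Design table into line.
- State the power behind 240 and the model used: period effects or none, a constant or a separate follow-up effect, and the correlation structure.
- As a clarification, say which post-hoc inputs were estimated from PADL data and which were carried over from the first calculation.

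The cost is a few sentences. Enrolment and analysis do not change. The stated attrition allowance becomes slightly less favourable.
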